6.1 Device Description

The Venus Versa system is a multi-application device intended to be used in aesthetic and cosmetic procedures.

The Venus Versa system consists of a console and 4 detachable applicators that deliver optical energy in the form of Intense Pulsed Light to the patient skin. The intense pulsed light lamp delivers non-coherent light distributed over a range of wavelengths from 500 nm to 1200 nm. Different filters are embedded in the different applicators so that each applicator can deliver the desired spectrum according to the indications to be treated.

The energy delivered to the patient's skin is used to treat various conditions via the mechanism of Selective Photothermolysis. The selective absorption of different wavelengths by the skin and its components (e.g. blood vessels, hair follicles, etc.) lead to localized heating and thermal lysis of the anatomic target. The different applicators use optical filters to optimize the energy delivered to the body, and match the spectrum of light delivered to the intended clinical application.

Figure 1: Venus Versa aesthetic treatment system and HR 690 applicator

The applicator that will be used for this study (HR 690) has a wavelength of 690 nm and has a spot size (treatment area) of 30 mm by 10 mm. The clinician is able to control the settings of IPL from the user interface (LCD GUI) display on the main console.

IPL settings: The available settings for this applicator are:

- Wave Length 690 nm.
- Spot size 30mmX10mm.
- Pulse duration of 20 – 50 ms.
- Fluence/Energy density of 5-20 J/cm².
- Pulse repetition rate of up to 3 Hz.

6.2 Measurement Equipment

6.2.1 Standard High Resolution Digital Camera

The investigative site will ensure the digital photography equipment is available for use during this study. Venus Concept will supply photo storage media for use with the digital camera during the study which must be returned to Venus Concept upon conclusion of the study. Digital photographs will be provided by the site to Venus Concept on compact flash cards, CD-ROMS, or similar media.

Photographs of the treated areas will be taken at various visits as detailed in the schedule of events chart.

Level of improvement and satisfaction

Subject's Improvement and Satisfaction with treatment will be recorded by a 5-point Scale: 1=None; 2=Slight; 3=Moderate; 4=Good; 5=Very Good.

Table 1– Clinical Evaluation Tools and appendix I.

For consistency purposes, all images throughout the study must be taken, using the same camera and lighting settings, preferably by the same photographer, the photography should be taken from the same angle.

Subject anonymity will also be assured for the images by deleting any ID detail. Only the code for the Case Number in the study will appear on the records being transferred to the sponsor.

6.2.2 Labels for hair count

Customized hair count sticker templates will be supplied by the sponsor. Templates consist of a rectangular frame sticker with a rectangular window sized 3*3 cm. The sticker template will be placed directly on the skin and the hairs in this window will be counted at specific visits during the study as detailed in section 7.2.1.1. For identification, the subject's ID, treatment area and visit date shall be filled out on the designated area upon the template frame. These photographs will be evaluated and counted by 2 blinded reviewers.

7 Study Procedures

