7.2.1.2 Hair reduction assessment

Hair counts will be accomplished by analysis of photographs. The original image of the photographs will be saved and archived in its original form by the site and a copy will be sent to the sponsor. The image will be enlarged to a uniform size to facilitate counting and the file shall be saved (locked) into a PDF format.

At baseline, immediately before treatment 3 and 6, 1M FU1, 3M FU2 and 6M FU3, a copy of the image shall be printed. Each image will be reviewed by the investigator or his/her designees. Additional copies of baseline, 1M FU1, 3M FU2 and 6M FU3 will be sent to two other reviewers who are blinded to the treatments. The reviewer will mark each hair identified with a red pen, and each of these marks will be tallied to obtain hair count. For a detailed hair count explanation please refer to section 7.4.2.2.

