7.3.2 Subject Identification

At enrollment each subject will receive a unique identifying number that will be composed of a consecutive number and his/her initials. This unique identifier will be used throughout the entire study and will be entered in the subject's CRF for each treatment and photographs.

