7.4.2 Photography and hair count

7.4.2.1 Photography

Photographs are mandatory for this research; they may also be used by the Sponsor (Venus Concept Ltd.) for future educational and marketing purposes.

Photographs will be taken prior to treatment and throughout the study according to specified time points detailed in Table 1, utilizing standard scientific equipment.

The photos should be taken in a private room or area of the clinic under controlled conditions, including the distance, angle, background and lighting in order to achieve high-quality before & after sets. Do not use direct illumination. The subject should be placed in the same position each time. As each photograph is taken, it should be viewed to ensure that it is in focus and is similar to its baseline counterpart in all technical aspects, including lighting, distance and angle.

For consistency purposes, the same person should ideally take all study photographs, especially per subject. The digital files should follow a consistent standard naming scheme, for example: 001TM_Tx1_right axillae.

In each photography session the order of photos should be as follows:

1. First photo is of the whole treatment area including a small sticker with the subject initials and date.
2. A close up photo graph including the hair count sticker template as detailed in the section below.

Effort will be made to ensure subject privacy when taking photographs of the groin/ bikini area. Black uniform undergarment should be used when photographing the treatment area.

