7.4.2.2 Hair count

The customized hair count sticker templates detailed in section will be supplied by the sponsor. Templates consist of a rectangular frame sticker with a one square inch rectangular window (25.4mm x 25.4mm). The sticker template will be placed directly on the skin and the hairs in this window will be counted at specific visits during the study as detailed in section 7.2.1.1. For identification, the subject's ID, treatment area and visit date shall be filled out on the designated area upon the template frame.

The following procedure is intended to ensure that the template is placed in the same position during subsequent visits:

7.4.2.2.1 Baseline visit (prior to the 1st treatment):

1. The appropriate treatment area will be decided.
2. The hair in the area to be treated will be scissor trimmed to 2 mm to facilitate hair counts for photography.
3. The template will be completed with the subject ID, treatment area and date.
4. The template will be placed directly on the skin, in the area to be treated.
5. A clear transparency sheet will be placed over the treatment area, over the template.
6. The transparency sheet will be marked with a permanent marker to indicate anatomical landmarks and the sticker template location.
7. A general photograph of the sticker template, overlaid with the transparency sheet will be taken, as well as a close-up picture.
8. The transparency sheet will be removed and an additional close-up picture of the sticker template will be taken for the baseline hair count.

7.4.2.2.2 "Hair count" treatment visits [3, 6, 1M±7D FU1, 3M±7D FU2 and 6M±7D FU 3]:

1. The hair in the area to be treated will be scissor trimmed to 2 mm to facilitate hair counts from photography.
2. The template will be completed with the subject ID, treatment area and date.
3. The sticker template will be placed on the area to be treated using anatomical landmarks and the baseline picture to properly position the transparency sheet prepared in the baseline visit.
4. A close-up photograph of the sticker template will be taken.
5. The sticker will then be removed, the area shaved to the skin surface and treatment performed.

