8.3 Study Analysis

The objective of this clinical study is to evaluate the safety of hair removal and to verify hair removal and permanent hair reduction using the Versa HR 690 nm applicator assessed by hair counts. For this purpose an average of hair count of 2 blinded reviewers will be done at baseline, following treatments, and at follow up visits. In case of a big discrepancy between 2 blinded reviewers, the hair count will be redone by a third blinded evaluator.

An intermediate safety report will be produced based on analysis of data collected post treatment number one of all the enrolled subjects. A Hair Removal report will be produced based on analysis of data collected at the three-month follow-up visit and a Permanent Hair Reduction report based on the analysis of data collected at the six-month follow-up visit will be the final report. The interim reports will not affect the continuation of the study. The study will regardless of the interim report results, be finalized according to this protocol.

The study reports will provide information for use in research & development, and future planned study. All statistical tests will be two-sided. The level of statistical significance for effectiveness analyses is five percent for all tests of differences. Paired t-test and/or Wilcoxon signed rank test will be used to compare the evaluations at the baseline and follow up sessions. Descriptive statistics and correlations between variables will be performed.

Safety: Adverse events reported will be listed, documenting course, outcome, severity, and possible relationship to the treatment.

9 Adverse Events

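### The plan does not say how the hair-count reviewers are kept unaware of visit, and the photographed template carries the visit date

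*Combined protocol and SAP*

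**What the plan says.** The design is single-arm and baseline-controlled, and is called blinded (section 2). Section 4.1 defines both primary endpoints as percent change in photographic hair count from baseline, at FU2 (3 months) and FU3 (6 months). Section 8.3 bases the evaluation on the two reviewers: "an average of hair count of 2 blinded reviewers will be done at baseline, following treatments, and at follow up visits".

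These statements bear on what the reviewers can see:

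- Section 6.2.2, after requiring the subject ID and treatment area on the template: "visit date shall be filled out on the designated area upon the template frame. These photographs will be evaluated and counted by 2 blinded reviewers". Section 7.4.2.2 repeats the labelling at baseline and at each later count visit.
- Section 7.4.2.2, on the image that is counted: "an additional close-up picture of the sticker template will be taken for the baseline hair count".
- Section 7.2.1.2, the only place that says what the blinding covers: "Additional copies of baseline, 1M FU1, 3M FU2 and 6M FU3 will be sent to two other reviewers who are blinded to the treatments". The image handling it describes is enlarging, locking as PDF, printing and copying.
- Section 7.4.2.1, on file names: "The digital files should follow a consistent standard naming scheme, for example: 001TM_Tx1_right axillae".
- Section 6.2.1, on anonymity: "deleting any ID detail. Only the code for the Case Number in the study will appear on the records being transferred to the sponsor".
- Section 7.3.2, on the subject number: "This unique identifier will be used throughout the entire study".

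On timing, Appendix I places the blinded counts after the study. Section 8.3 plans an interim document: "A Hair Removal report will be produced based on analysis of data collected at the three-month follow-up visit".

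**The concern.** All subjects receive the same device, so there is no treatment allocation to conceal. What a reader could know, and what could influence the count, is whether an image was taken before or after treatment. The plan puts a date on the object being photographed, sends those photographs to the reviewers, and describes no step that hides the date or breaks the link between a subject's images.

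Marking hairs trimmed to 2 mm on a print with a red pen is a judgement task. A reader who expects fewer hairs after treatment may mark fewer. Averaging two readers does not cancel an expectation they share, and the third evaluator is called only when the two disagree. Without a concurrent control, nothing in the analysis separates such a shift from a treatment effect. What is at stake is the size and credibility of the reported reduction at FU2 and FU3.

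**Working it through.** The plan gives no figure to reproduce here: no expected photographic baseline count, variance, reader error or success threshold. The check is a comparison of sections, followed by arithmetic with its assumptions labelled.

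**1. Can a reader tell baseline from follow-up?**

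| Step | What the plan provides | Does it hide the visit? |
|---|---|---|
| Template label (6.2.2, 7.4.2.2) | ID, area, date | No; it shows the visit date |
| Image processing (7.2.1.2) | Enlarge, lock, print, copy | No |
| File name (7.4.2.1) | Example contains a treatment number | No, if the reviewer sees it |
| Anonymity rule (6.2.1) | Removes ID detail; case code only on records sent to the sponsor | Possibly; date and visit are not mentioned |
| Identifier (7.3.2) | One number for the whole study | No; it links a subject's images |
| Reading order | Not described | No |

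If dates are visible and images are linked by subject, the baseline image is easy to identify. Gap from baseline to FU1, taking one month less or plus 7 days as 3.3 or 5.3 weeks:

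- Shortest: 5 × 4 + 3.3 = 23.3 weeks.
- Longest: 1 (Visit 0 to first treatment) + 5 × 6 + 5.3 = 36.3 weeks.

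**2. How an under-count enters the endpoint.** Let B be the baseline count, C the follow-up count and u the hairs missed at follow-up because of expectation. Then (C − u − B)/B × 100 = (C − B)/B × 100 − 100u/B, so the apparent reduction grows by 100u/B percentage points. B and u are assumed:

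| B | u = 1 | u = 3 |
|---|---|---|
| 60 | 1/60 = 1.7 | 3/60 = 5.0 |
| 100 | 1/100 = 1.0 | 3/100 = 3.0 |

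The one count in the documents is the eligibility floor of more than 15 hairs, by the investigator's manual count (5.2.1). At 16 hairs, one hair is 100/16 = 6.25 points. The range in the table is therefore not an upper bound.

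**3. Would the planned test guard against this?** It would not, because a paired test responds to any mean shift. The table gives the chance of a significant result in a two-sided 5% paired t-test (noncentral t) if the true change were zero and reading alone produced the shift. The SDs of percent change are assumed:

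| Shift | n | SD 10 | SD 20 | SD 30 |
|---|---|---|---|---|
| 5 points | 120 | about 100% | 78% | 44% |
| 5 points | 40 | 87% | 34% | 18% |
| 2 points | 120 | 58% | 19% | 11% |
| 2 points | 40 | 24% | 10% | 7% |

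Unbiased reading gives 5%. A zero true change is a stress case and not an expectation for this device.

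**The case against.** The strongest reply has four parts.

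- **Meaning of the blinding phrase.** Treatments, in the plural, usually means the six sessions in this protocol. Being blinded to them could mean not knowing whether they have been given, which is masking to visit. This is a fair reading, but it supplies no mechanism and sits badly with a dated label on the counted image.
- **The anonymity rule.** Read literally, allowing only the case code on records sent to the sponsor excludes a date. It may well do so in practice, which is why visibility is stated as likely and not certain. But the rule is written for privacy, 7.2.1.2 does not say the reviewers' copies come from that set, and the case code still links a subject's images.
- **Weak or omitted evidence.** The file name is only an example, and reviewers appear to work on prints where it may not show. The file name is therefore secondary evidence. Uniform trimming and enlargement, marking each hair and the third evaluator do make counts more consistent and auditable, but none of them hides the visit.
- **Assumed numbers and partial benefit.** The magnitudes are illustrative, a small reading bias would not explain a large true reduction, and visible hair loss may reveal some follow-up images anyway. All of this stands. It limits the claim but gives no reason to leave a written date in view.

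Two narrower points also stand. Section 8.3 already largely assigns the primary evaluation to the blinded counts, so only a clarifying sentence is needed there. The timing of the Hair Removal report is a separate, minor matter: 8.3 gives no issue date, so it is in tension with Appendix I but does not strictly contradict it.

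**Conclusion.** The concern holds and should be fixed. Followed as written, the plan can reveal baseline versus follow-up to the reviewers, and that is the only contrast in the study. Whether they would actually see the date is likely but not established; confidence is medium, because the anonymity rule might remove it.

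The size of any bias cannot be derived from the documents. The range of 1 to 5 percentage points rests on assumed baselines of 60 and 100 hairs and assumed under-counts of 1 to 3, and it would be larger near the eligibility floor. The plan states no success threshold, and no change of conclusion is claimed.

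**What to change.** In 6.2.2 and 7.2.1.2, state that before images go to the two reviewers, and to the third if used:

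- the frame label is cropped or masked;
- file names and identifiers are replaced by random codes;
- baseline and follow-up images are presented in random order, mixed across subjects;
- the key is held by existing study staff who do not count.

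In 8.3, add that both primary endpoints use only these counts, since study personnel also count the same images. Reconcile 8.3 with Appendix I on timing. The simplest way is to issue the Hair Removal report's hair-count results after the single post-study read. If FU3 were read later as its own batch, the batch itself would disclose the visit.

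**Cost.** The readers, visits and sample size do not change. Images to prepare over four blinded-count visits:

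- One site per subject: 120 × 4 = 480.
- Every treated side, with 40 subjects per group: 40 × 4 (axillae and bikini sides) + 40 × 2 (thighs) + 40 × 1 (back or abdomen) = 280 sites; 280 × 4 = 1,120.

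The plan does not say which applies. Waiting for the post-study read delays the Hair Removal hair-count results by at least the FU2-to-FU3 gap, 91 ± 14 days = 77 to 105 days, or 11 to 15 weeks, plus counting time. That delay already follows from the Appendix I schedule and is not caused by the masking. Visible hair loss or skin change may still identify some follow-up images, so the change reduces the risk without removing it.

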7.1 Study duration and timelines

Each subject will be enrolled and scheduled for six treatments at approximately four to six week intervals upon re-growth of hair and return for follow-up visits at one month FU1 (\pm seven days) three month FU2 (\pm seven days) and six month FU3 (\pm seven days) after the last treatment for evaluation of the treated areas. During each visit various tasks will be performed as detailed in the study flow chart.

Level of improvement and satisfaction

Subject's Improvement and Satisfaction with treatment will be recorded by a 5-point Scale: 1=None; 2=Slight; 3=Moderate; 4=Good; 5=Very Good.

Table 1– Clinical Evaluation Tools.

Each subject will therefore participate in the study for a period of at least 11 months. The study is anticipated to be completed within twelve months.

7.2 Evaluation Assessments

Various assessments will be performed throughout this clinical study. The hair count that is done on the photographs of the treated area will be performed by 2 blinded evaluators.

7.2.1.1 Post Treatment Responses

Immediate and short term responses (erythema, edema, purpura, etc.) will be assessed for severity immediately and up to 30 min post treatment, by a 5 level scale: 1=none; 2=trace; 3=moderate; 4=marked; 5=severe.

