Main Inclusion Criteria	
 • Healthy adults, females or males older than 21 years of age with skin type V-VI; hair color Black or dark brown; having a suitable treatment area for hair removal. Two small anatomical areas (right and left axillae and double sided bikini line) or; • One double sided large area (right and left thighs)or; • One large area (whole back / abdomen) 
Other areas not defined above, as face, are not allowed to be treated.
	
Main Skin Related Exclusion Criteria	
 • Active infections in the treatment area. • Dysplastic nevi in the treatment area. • Tattoos in the treatment area. • Significant concurrent skin conditions or any inflammatory skin conditions in the treatment area. • Active cold sores, open lacerations or abrasions in the treatment area. • Chronic or cutaneous viral, fungal, or bacterial diseases. • Deep suntan, recent suntan, sunburn or artificially tanned skin. • Current skin cancer. • History of skin cancer or pre-cancerous lesions at the treatment areas. 	

Investigational Treatment and Study Duration	Each subject will receive six treatments at four to six weeks intervals and return for follow-up visits at one (\pm seven days), three (\pm seven days) and six (\pm seven days) months after the last treatment for evaluation of the treated areas.
Criteria for Evaluation	
Primary endpoints
 
 • Hair count reduction from photographs 3 months following the last treatment - FU2, as compared to baseline (hair removal) • Hair count reduction from photographs 6 months following the last treatment - FU3, as compared to baseline (permanent hair reduction) 
Secondary endpoints
 
 • Hair count reduction from photographs 1 month following the last Treatment - FU1 • Subject's assessment of comfort associated with treatments using a VAS scale, following each of the 6 treatments. • Subject's satisfaction with hair removal treatments and assessment of improvement using a five point scale, at visit 3, 6, 7, 8 & 9. • Immediate response following each treatment, defined as type and intensity of response and the time it takes for it to subside. Should be removed any adverse events associated with various setting used during the treatment and follow-up period.

Table of Contents

1	Introduction.....	8
1.1	Background.....	8
1.2	Rationale for Evaluation	8
2	Study Design.....	9
3	Study Objectives.....	9

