4.3 Safety Endpoint

- Immediate response following treatment, defined as intensity of response and the time it takes for it to subside.
- Any adverse events associated with various setting used during the treatment and follow-up period.

5 Patient Population

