5.1 Source and Sample Size

Subjects shall be recruited by the investigator from within the investigator's patient population. Subjects shall be with skin types V-VI and have visible hair at the designated treatment area.

Each site participating in this study will enroll up to 12 subjects according to the inclusion/exclusion criteria. Each subject (120 subjects) included for treatment will receive six treatments at four to six week intervals upon re-growth of hair and return for follow-up visits at one month FU1 (\pm seven days), three FU2 (\pm seven days) and six FU3 (\pm seven days) months after the last treatment for evaluation of the treated areas. Enrolled subjects that did not complete the full course of the study will be replaced.

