7.2.2.2 Level of improvement and satisfaction

Subject's Improvement and Satisfaction with treatment will be recorded by a 5-point Scale: 1=None; 2=Slight; 3=Moderate; 4=Good; 5=Very Good.

Table 1– Clinical Evaluation Tools

Claim/task	When to conduct?	Tool
Photography	Baseline, immediately before treatments 3, 6, 1M±7D FU1, 3M±7D FU2 and 6M±7D FU 3	Standardized digital photographs
Hair count by single study personnel	Baseline, immediately before treatments 3, 6, 1M±7D FU1, 3M±7D FU2 and 6M ±7D FU3	Standardized digital photographs
Hair count by blinded reviewers	Baseline, 1M ±7D FU1, 3M ±7D FU2 and 6M ±7D FU3	Standardized digital photographs
Immediate and short term response	Immediately following treatments 1-6	Examination of skin in the treated area based on 5 level scale
Subjects comfort assessment	Immediately following treatments 1-6	VAS
Subjects improvement/satisfaction assessment	Treatments 3, 6, 1M ±7D FU1, 3M ±7D FU2 and 6M ±7D FU3.	5 point scale
Safety	Throughout study	Examination of skin in the treated area, interview subjects

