7.6 Post-treatment Instructions

7.6.1 Post treatment

The assessment of pain based on the subject's report will be documented immediately after each treatment test spot in the anatomical area treated. The Investigator should also examine and record the skin immediate response following treatment.

Cold packs may be placed on the treated area for post-treatment cooling. On the night following treatment, subjects should generally avoid hot water, cleanse their skin gently with tepid water, and hydrate the skin with a suitable moisturizer.

Subjects should be aware that post-treatment erythema, edema and some discomfort of the treated areas are possible and should not be a cause for concern. They may also experience some purpura in the treated areas which would be expected to resolve within several days.

Subjects will have to be instructed not to tweeze, pluck, wax, use depilatory creams, or any other hair removal methods in the treated areas throughout the evaluation. Seven days prior to each treatment and follow-up visits subjects shall not shave the treatment areas in order to obtain accurate hair counts.

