9.1.6 Anticipated Outcome Related Adverse Events

Anticipated adverse events in this study may include: blistering, burns, excessive edema or erythema (excessive considered as edema or erythema that do not resolve within 2-3 days), infection, PIH and scarring.

Any anticipated AE that occurs at any time during or after the use of the study device must be reported by the Investigator to Venus Concept. If the anticipated AE, in the opinion of Venus Concept or the Investigator, is likely to affect the safety of the subjects or the conduct of the study, the IRB/ Helsinki/ other ethic committee will be notified of the effect within 10 working days after Venus Concept first receives notice of it. In this study if an adverse event of PIH occurs the Investigator will continue following the subject until the PIH is resolved or up to 6 months following the last visit, whichever comes first.

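### Time for the skin response to subside is part of the safety endpoint, but no scheduled assessment captures it beyond 30 minutes after treatment

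*Combined protocol and SAP*

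**What the plan says.** Section 4.3 gives the safety endpoint as: "Immediate response following treatment, defined as intensity of response and the time it takes for it to subside". The synopsis lists the same item among the secondary endpoints, after each treatment, "defined as type and intensity of response and the time it takes for it to subside". Both include a duration.

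The measurement sections do not provide one:

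- Section 7.2.1.1 says immediate and short-term responses "will be assessed for severity immediately and up to 30 min post treatment", on a scale from 1 (none) to 5 (severe). It names no time variable.
- Table 1 (section 7.2.2.2) places this assessment "Immediately following treatments 1-6".
- Section 7.6.1 adds: "The Investigator should also examine and record the skin immediate response following treatment".
- Section 5.1 plans "six treatments at four to six week intervals upon re-growth of hair", after which subjects "return for follow-up visits at one month FU1", with a window of ±7 days. The Appendix I flow chart shows no contact between these visits.

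Two other sections expect reactions that last for days. Section 9.1.6 lists excessive edema or erythema among the anticipated adverse events, with "excessive considered as edema or erythema that do not resolve within 2-3 days". Section 7.6.1 expects any purpura to take several days to clear.

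The safety analysis in 8.3 is a listing of adverse events. It has no analysis of time to subside and no rule for responses still present at the last look.

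**The concern.** The endpoint has two components and the schedule serves only one of them. Intensity is graded within 30 minutes. Time to subside is observed only for responses that clear within those 30 minutes. For the rest, the plan has no diary, call or early return visit, and the next scheduled look is weeks away, when a reaction lasting a few days will have gone.

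Safety is a primary objective (3.1), and section 1.2 describes darker skin as the harder case to treat. The protocol also uses duration to describe which erythema or edema is excessive, so the missing quantity bears on adverse-event classification as well as on a descriptive summary. The intermediate safety report in 8.3 draws on data collected after treatment 1. Unless it waits for visit 2, its scheduled skin-response data stop at 30 minutes. Durations that nobody recorded at the time cannot be reliably recovered later.

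**Working it through.** The plan ties no sample size, power or error rate to this endpoint and states no figure to reproduce. The check compares the observation schedule with the protocol's own time scales.

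**Inputs**

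- Scheduled observation: 30 min = 0.5 h (7.2.1.1).
- Description of excessive erythema or edema: 2-3 days = 2 × 24 to 3 × 24 = 48-72 h (9.1.6).
- Next visit after treatments 1-5: 4-6 weeks = 28-42 days = 672-1,008 h (5.1, Appendix I).
- Next visit after treatment 6: 1 month ±7 days. Taking a month as 30 days (assumption), 23-37 days = 552-888 h.
- 120 subjects with six treatments each (5.1).

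**Step 1: description against window.** 48 / 0.5 = 96 and 72 / 0.5 = 144. The 2-3 day line lies at 96 to 144 times the length of the scheduled look.

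**Step 2: the unobserved interval.** It runs from 0.5 h to 672-1,008 h after treatments 1-5, and from 0.5 h to about 552-888 h after treatment 6. Both contain the whole of 48-72 h.

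**Step 3: sessions.** 120 × 5 = 600 are followed by the 4-6 week gap and 120 × 1 = 120 by the one-month gap, giving 720 planned sessions.

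**Step 4: what the plan yields for each response.**

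- Clear by 30 min: duration known to be at most 30 min.
- Present at 30 min and gone at the next visit: duration known only to lie between 0.5 h and that visit, unless the subject recalls a date.
- Recorded as an adverse event: 9.1 requires onset and resolution dates. If the event cleared between visits, the schedule offers only the subject's account for the second date.

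**Step 5: illustration.** The documents give no distribution of durations. Assume exponential resolution times with median *m* hours. The share resolved by 30 min is 1 − 0.5^(0.5/*m*):

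| Assumed median *m* | Resolved by 30 min |
|---|---|
| 0.25 h | 75% |
| 0.5 h | 50% |
| 1 h | 29% |
| 2 h | 16% |
| 6 h | 6% |
| 24 h | 1.4% |
| 48 h | 0.7% |

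Whatever the shape of the distribution, the median lies inside the observed window only if at least half of the responses clear within 30 minutes.

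**The case against.** The protocol has more than the 30-minute look. Table 1 lists safety throughout the study, by skin examination and subject interview. Section 9.1.6 requires any anticipated adverse event to be reported whenever it occurs, and 9.1 requires its resolution date. Test spots are assessed after at least 2 hours (7.4.3). The case report forms are not in the documents, so a field for resolution time cannot be excluded. The synopsis ranks this response as secondary, and no test, sample size or stopping rule uses it.

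Much of this stands, and it rules out some stronger readings:

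- A reader might infer that time to subside cannot be measured at all. That goes too far. Responses that clear within 30 minutes can be timed, and recorded adverse events carry dates.
- A reader might infer that erythema or edema counts as an adverse event only after 2-3 days. Section 9.1.6 defines the word excessive within a non-exhaustive list, and the general definition in 9.1 is broader.
- A reader might infer that excessive reactions will be under-counted. Section 7.6.1 does tell subjects not to worry about redness and swelling, which could discourage reporting. But recall error can misclassify in either direction, and the documents do not settle which.
- A reader might want a count of affected durations. That needs the share of responses present at 30 minutes, which the documents do not give. Sessions are also not reactions, since one session may produce none or several.

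The objection does not supply a scheduled observation. Interviews take place at visits weeks later. The test-spot check does not concern the full treatment. A resolution field on a form would still lack a scheduled look to fill it.

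**Conclusion.** The point holds as an inconsistency between endpoint and schedule. Followed as written, the plan captures time to subside by scheduled assessment only up to 30 minutes. Later resolution rests on recall or on adverse-event dates, and the 2-3 day description in 9.1.6 lies wholly inside the unobserved gap. The gap follows up to 720 planned sessions, which counts sessions and not lost durations. The conclusion depends on the schedule in the documents and on no instrument existing outside them; the 30-day month affects only the treatment 6 figures. The exponential table is illustrative and the conclusion does not rest on it. The efficacy analyses are unaffected. This is worth correcting because the fix is cheap.

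**What to change.** 1. In 7.2.1.1 and Table 1, record for each response whether it has resolved by 30 minutes, alongside its severity grade.
2. Give subjects a take-home card after each treatment. For the first several days they note daily whether redness, swelling or purpura is still present, and the date it cleared. Collect the card at the next scheduled visit, where the investigator uses it in the adverse-event assessment under 9.1. The card informs that assessment and does not replace it.
3. In 8.3, report the proportion resolved by 30 minutes and tabulate the recorded day of resolution, treating missing dates as censored. A simple table is enough.
4. Reconcile the 2-3 day range in 9.1.6 to a single definition. Which one is for the sponsor to decide.

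The alternative to items 2 and 3 is to limit the endpoint in 4.3 and the synopsis to the 30-minute window and report responses unresolved at 30 minutes as such. That removes the inconsistency in the endpoint, but the 9.1.6 description would still rest on recall and adverse-event reporting.

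The cost is one card and short edits to 7.2.1.1, Table 1 and 8.3, with no extra visit or assessor. The data would be subject-reported, up to 720 cards would have to be collected and entered, and a card returned at the next visit gives no early notice of a reaction.
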